6.5 STATISTICAL ANALYSIS

All statistical analyses will be performed using Statistical Analysis System (SAS), R, or S-Plus statistical software. No formal multiple comparison adjustments will be employed for safety endpoints or secondary endpoints.

6.5.1 Analysis Variables

The analysis variables consist of baseline variables and safety variables for primary and secondary objective analyses.

6.5.2 Baseline Demographics

Baseline characteristics including demographics and laboratory measurements will be summarized using descriptive statistics.

6.5.3 Safety Analysis

6.5.3.1 Reactogenicity

The number and percentage of participants experiencing each type of reactogenicity sign or symptom will be tabulated by severity. For a given sign or symptom, each participant's reactogenicity will be counted once under the maximum severity for all assessments.

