3. STUDY OBJECTIVES

3.1 PRIMARY OBJECTIVES

- To evaluate the safety and tolerability of the HA-F A/Sing vaccine, administered as a single dose at 20 mcg IM via needle and syringe at Day 0 to healthy adults.
- To evaluate the safety and tolerability of the HA-F A/Sing vaccine, administered at 60 mcg IM via needle and syringe to healthy adults by repeat dosing at Day 0 and Week 16 for a total of 2 injections.
- To evaluate the safety and tolerability of the DNA A/Sing vaccine, administered as a single dose at 4 mg IM via needle-free injection device at Day 0 to healthy adults in the prime-boost regimen.

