6.3 ENDPOINTS

6.3.1 Primary Endpoints: Safety

Assessment of product safety will include clinical observation and monitoring of hematological and chemical parameters. Reactogenicity will be closely monitored for 7 days after each injection and safety evaluated by clinical visits throughout 40 weeks. See Section 4.2 and Appendix II for details and specified time points.

The following parameters will be assessed for all study groups:

- Occurrence of solicited local reactogenicity symptoms for 7 days following each injection
- Occurrence of solicited systemic reactogenicity symptoms for 7 days following each injection
- Change from baseline in safety laboratory measures
- Occurrence of AEs of all severities through the “Week 4” visit after each injection
- Occurrence at any time throughout the study of SAEs or new chronic medical conditions that require ongoing medical management.

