6.5.3.2 Adverse Experiences

Adverse experiences are coded into Medical Dictionary for Regulatory Activities (MedDRA) preferred terms. The number and percentages of participants experiencing each specific AE will be tabulated by severity and relationship to treatment. For the calculations in these tables, each participant's adverse experience will be counted once under the maximum severity or strongest recorded causal relationship to treatment.

A complete listing of adverse experiences for each participant will provide details including severity, relationship to treatment, onset, duration and outcome.

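### As written, the maximum-severity rule for solicited symptoms merges the DNA prime with the HA-F boost in Group 3, so the planned table cannot give the reactogenicity rate of the single DNA dose

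*Combined protocol and SAP*

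**What the plan says.** **Endpoints.** Section 6.3.1 defines the solicited endpoints per injection: "Occurrence of solicited local reactogenicity symptoms for 7 days following each injection" and "Occurrence of solicited systemic reactogenicity symptoms for 7 days following each injection". AEs of all severities are counted through the Week 4 "visit after each injection". The list opens with "The following parameters will be assessed for all study groups".

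**Counting rules.** Section 6.5.3.1 tabulates each solicited sign or symptom by severity, where each participant's "reactogenicity will be counted once under the maximum severity for all assessments". Section 6.5.3.2 has a similar rule for AEs, under which each participant's "adverse experience will be counted once under the maximum severity or strongest recorded causal relationship to treatment". It adds a listing: "A complete listing of adverse experiences for each participant will provide details including severity, relationship to treatment, onset, duration and outcome". Nothing in Section 6.5.3 splits a table by injection, product or group.

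**Objectives.** Section 3.1 has three primary objectives: HA-F 20 mcg as one dose, HA-F 60 mcg as a two-injection regimen, and "To evaluate the safety and tolerability of the DNA A/Sing vaccine, administered as a single dose at 4 mg IM". Section 6.2 restates the third at regimen level, as DNA prime plus HA-F boost.

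**Design.** Under Table 2 (Section 4), Group 1 has one HA-F injection, and Groups 2 and 4 have two. Group 3 has DNA by needle-free device at Day 0 and HA-F by needle and syringe at Week 16, with 10 participants in each of two age cohorts.

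**The concern.** The endpoint is per injection, but the analysis rule is per participant. Where both injections are the same product, the result is a regimen-level summary. In Group 3 the two injections differ in product and in device, so one worst value mixes two different exposures. A participant with Grade 1 pain after DNA and Grade 2 pain after HA-F appears only as Grade 2, and the DNA reaction leaves the table.

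No other group can supply the DNA rate. Attribution cannot supply it either: Section 5.1 has paper-diary data entered without attribution and asks for attribution only for unsolicited AEs.

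The question is a live one. The trial is the first human use of DNA A/Sing (Section 1.3), no preclinical toxicology was done on this product (Section 2.5), and Section 8.5.2 states that it is unknown whether side effects with PharmaJet will match those seen with the earlier device.

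**Working it through.** **1. The plan's own precision figures.** The exact 95% upper bound at zero events is 1 − 0.025^(1/n). For n = 5 this is 0.522 and for n = 10 it is 0.308, both as in Table 6-2. For Group 3 with its age cohorts combined (n = 20, if all receive the injection) it is 0.168. The counting rule itself has no stated figure to reproduce.

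**2. What a merged Group 3 count says about DNA.** Let *a* be the number with a symptom after DNA, *b* the number after HA-F, and *m* the number after either. The rule reports only *m*. Since *a* ≤ *m* and *b* can be as large as *m*, any *a* from 0 to *m* is possible. As an illustration, take *m* = 8 of 20:

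| DNA count compatible with 8/20 merged | Exact 95% CI |
|---|---|
| 0/20 | 0 to 0.168 |
| 4/20 | 0.057 to 0.437 |
| 8/20 | 0.191 to 0.639 |

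The intervals for the two extremes do not overlap.

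**3. The same point in rates.** The documents give no per-injection rates, so these are assumed. With rates p1 (DNA) and p2 (HA-F), the merged rate is 1 − (1 − p1)(1 − p2) if the injections are independent. Under any dependence it lies between max(p1, p2) and min(1, p1 + p2).

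| DNA, HA-F | Independent | Range under any dependence |
|---|---|---|
| 0.1, 0.3 | 0.37 | 0.30 to 0.40 |
| 0.2, 0.2 | 0.36 | 0.20 to 0.40 |
| 0.3, 0.5 | 0.65 | 0.50 to 0.80 |

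Under independence, the first two rows give almost the same table entry although the DNA rate doubles.

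**4. One injection against two.** For equal per-injection risk p, Group 1 shows p. Group 2 shows a rate between p and min(1, 2p), or 1 − (1 − p)² under independence.

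| p (Group 1) | Group 2, independent | Group 2, range |
|---|---|---|
| 0.2 | 0.36 | 0.2 to 0.4 |
| 0.4 | 0.64 | 0.4 to 0.8 |
| 0.6 | 0.84 | 0.6 to 1 |

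With the same risk per injection, Group 2 can look equal or worse, never better. The size of the gap depends on within-participant correlation, which the documents do not give. It may be zero.

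**The case against.** **The rule may mean the worst daily grade within one 7-day window.** Diary symptoms are recorded daily, so each window holds several assessments, and the per-injection endpoint favours this reading. It is possible, but Section 6.5.3.1 does not say it. The sentence sets no window, and its plain sense covers every assessment a participant has. One added phrase would settle it.

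**Section 6.2 treats DNA as part of a regimen.** It does, and a regimen-level maximum would answer that version. Section 3.1 still names the single DNA dose, so the two sections need aligning; the restatement does not cancel the objective.

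**AEs are better protected.** This stands in large part. Section 6.5.3.2 does not use the all-assessments wording. Its planned listing carries onset dates, and unsolicited AEs are recorded only to Week 4 after injections about 16 weeks apart, so each can be placed with its product. The listing is not stated to cover diary symptoms, and a listing is not a rate with a denominator. The AE side is a matter of consistency.

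**Stronger readings that a reader might infer.** Three are not supported:

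- *That one-dose and two-dose groups are pooled.* No section pools them. Section 6.3.1 refers to all study groups and Section 6.4.1 gives precision within each group. The gap is that by-group tables are never stated in Section 6.5.3.
- *That the primary safety objectives cannot be answered.* The 20 mcg objective involves one injection, and the 60 mcg objective is a two-injection regimen of one product. Both can be read from by-group tables. For DNA, the limit lies in the planned summary table; the diary data are collected after each injection.
- *That the rule creates a false dose effect of 16 to 24 points.* Those gaps require independent injections. The plan makes no formal 20 versus 60 mcg reactogenicity comparison, and the dose decisions are untouched: the Section 4.3 reviews take place two weeks after the fifth participant's vaccination, and the Group 2 boost depends on that review.

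**Conclusion.** The point holds for solicited symptoms in Group 3. On the literal reading of Section 6.5.3.1, the planned table cannot give the reactogenicity rate of the single DNA dose: the merged count bounds it above and leaves everything down to zero open. This follows from the counting rule alone and needs no assumption about correlation. The 8/20 example assumes the planned 20 participants all receive both injections.

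Two smaller consequences follow. The first- and second-dose profile of HA-F 60 mcg is not shown, and Group 1 and Group 2 percentages cover different numbers of 7-day windows.

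The data collected, the sample size, the dose-escalation reviews and the 20 mcg and 60 mcg regimen objectives are not compromised. This is an endpoint-to-table mismatch that is cheap to correct. It is better corrected in advance: assignment is open-label, so a split chosen later would be chosen with results in view.

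**What to change.** In Section 6.5.3.1, state that solicited symptoms are tabulated by group and by injection (after prime, after boost), with product and dose in the column heading. Count each participant once per symptom at maximum severity within that injection's 7-day window. Use participants who received that injection as the denominator, so that those who stop after the prime do not dilute the boost column. Keep the any-injection maximum as a separate overall column.

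For consistency, use the same layout in Section 6.5.3.2, with the window running through the Week 4 visit after each injection. Align the DNA objective in Section 3.1 with its regimen-level restatement in Section 6.2, so that it is clear whether a DNA-only summary, a regimen summary or both are intended.

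The cost is a few more table columns and revised wording. No data collection, visit or sample size changes.

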6.5.3.2 Adverse Experiences

Adverse experiences are coded into Medical Dictionary for Regulatory Activities (MedDRA) preferred terms. The number and percentages of participants experiencing each specific AE will be tabulated by severity and relationship to treatment. For the calculations in these tables, each participant's adverse experience will be counted once under the maximum severity or strongest recorded causal relationship to treatment.

A complete listing of adverse experiences for each participant will provide details including severity, relationship to treatment, onset, duration and outcome.

6.5.3.3 Local Laboratory Values

Boxplots of local laboratory values will be generated for baseline values and for values measured during the course of the study. Each boxplot will show the 1st quartile, the median, and the 3rd quartile. Outliers, or values outside the boxplot, will also be plotted. If appropriate, horizontal lines representing boundaries for abnormal values will be plotted.

6.5.4 Immunogenicity Analysis

The statistical analysis for immunogenicity will employ the intent-to-treat principle whereby all data from enrolled subjects will be analyzed according to the group assignment. However, if during immune assessment on stored samples, a subject is found to have a positive antibody response at baseline, the vaccine immune responses assessment for these subjects will not be included in the final immunogenicity analysis. If needed, a per-protocol analysis will be performed as secondary analysis where subjects will be analyzed according to their actual vaccination scheme if it is different from the assigned or up to the last visit in the study if there are early dropouts. The study is not designed to power the comparison in immune responses between vaccine dosages.

If assay data are qualitative (i.e., positive or negative) then analyses will be performed by tabulating the frequency of positive response for each assay at each time point that an assessment is performed. Binomial response rates will be presented with their corresponding exact 95% confidence interval estimates.

Some immunologic assays have underlying continuous or count-type readout that is often dichotomized into responder/non-responder categories. For these assays, graphical and tabular summaries of the underlying distributions will be made. These summaries may be performed on transformed data (e.g., log transformation) to better satisfy assumptions of symmetry and homoscedasticity.

6.5.5 Missing Data

Missing responses will be assumed to be missing completely at random. Analyses will include all samples available at each study time point.

6.5.6 Interim Analyses

Safety Reviews: The PSRT will review safety data routinely throughout the study. The study will utilize both electronic database features and reviews by designated safety review personnel to identify in a timely manner if any of the safety pause rules of the study are met.

Immunogenicity Review: The analyses of immunogenicity may be performed when the HAI assays of samples are collected at 4 weeks after the prime vaccination and at 2 weeks after the boost vaccine. This may occur prior to completion of safety follow-up visits or collection of data for secondary and exploratory immunogenicity endpoints. Such an analysis would constitute the final analysis for the primary immunogenicity endpoint, so sample size adjustments are not required. Reports providing results by study group may be provided to VRC solely for the purpose of informing decisions related to future trials in a timely manner. The results should in no way influence the conduct of the VRC 316 trial in terms of early termination or later safety or immunogenicity endpoint assessments. Analyses of secondary and exploratory immunogenicity assays may also be performed as data become available.

6.6 INTERVENTION ASSIGNMENTS

For Part I (*dose-escalation*): Subjects between 18-47 years will be assigned to the dose group that is open to accrual at the time of enrollment. When a subject is enrolled into a group but does not begin study injections or if a subject withdraws, a new eligible subject may be enrolled into the same group in order to complete the safety data set as planned.

For Part II (*prime-boost*): Subjects will be stratified by age and randomized equally into Group 3 or Group 4.

The subject and the study clinicians will be informed on the subject's randomization assignment upon completing of enrollment in Advantage Electronic Data Collection (AdEDC) system.

To decrease the potential for participant dropouts during the period between randomization and initial vaccination, randomization will occur on Day 0 after the study consent is signed and eligibility is confirmed. If subjects accrued to a study group do not complete the number of vaccinations and follow-up duration specified, then additional subjects may be accrued in that group.

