4.2.3 Enrollment and Randomization

Day 0 is defined as the day of protocol enrollment and first injection for all groups. Protocol-specific eligibility is reviewed on Day 0 as part of the enrollment process, but eligibility evaluations conducted during a screening visit are routinely used for eligibility if evaluations are within the specified window prior to Day 0. However, if clinical assessment on Day 0 suggests significant changes may have occurred since the screening visit, then evaluations done on Day 0 are used for eligibility. Day 0 evaluations and medical history prior to the first injection are the baseline for subsequent safety assessments.

Part I includes staged enrollment with required interim safety reviews before proceeding with the next dose group. In Group 1, five subjects will be enrolled with no more than one subject per day. Following dose escalation review, five subjects will be enrolled in Group 2 with no more than one subject per day. An internal safety review will determine whether enrollment can begin in Part II.

In Part II subjects will be stratified by age and randomized equally into Group 3 and Group 4. Neither the clinic staff nor the subjects will know in advance which group will be assigned to the enrollees in the study. The Protocol Statistician will prepare the randomization plan in advance and provide it to the site Pharmacy and Data Management Center.

The pharmacy database and study randomization will be set up prior to opening the study to accrual. The group assignment will become known to the staff and subject immediately after completing the electronic enrollment into the study on Day 0. The visit schedule is based on intervals of time after each study injection (Appendix II).

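### Section 6.6 lets non-completers in randomized Groups 3 and 4 be replaced within the same group, which conflicts with concealed allocation in 4.2.3 and weakens the regimen comparison

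*Combined protocol and SAP*

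**What the plan says.** Section 6.6 treats the two parts separately. For Part I, a subject who never starts injections or who withdraws can be replaced: "a new eligible subject may be enrolled into the same group in order to complete the safety data set as planned". For Part II: "Subjects will be stratified by age and randomized equally into Group 3 or Group 4". The last paragraph of 6.6 explains that randomization takes place on Day 0, after consent and confirmation of eligibility. It then adds a general rule for any study group: if its subjects "do not complete the number of vaccinations and follow-up duration specified, then additional subjects may be accrued in that group".

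Section 4.2.3 repeats the Part II randomization and adds concealment: "Neither the clinic staff nor the subjects will know in advance which group will be assigned to the enrollees in the study". The trial is open label once a subject is in: "The group assignment will become known to the staff and subject immediately after completing the electronic enrollment into the study on Day 0".

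Section 6.5.4 applies intent-to-treat to immunogenicity, so that "all data from enrolled subjects will be analyzed according to the group assignment". Section 6.5.5 uses whatever samples exist at each time point and assumes that missing responses are missing completely at random. Table 2 plans 40 subjects in Part II and permits up to 65, without saying how the extra places are divided between groups.

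**The concern.** The replacement sentence in 6.6 names no part of the study and follows directly on the randomization text. A subject recruited to fill a place in a particular arm has an arm that staff know before enrollment. That cannot be squared with 4.2.3, and nothing in the protocol reconciles the two.

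The trigger also arises after randomization and usually after the first injection. Section 4.4.1 lists reasons for stopping injections that include related adverse events and pregnancy, so failure to complete can depend on the assigned regimen. If it does, the two arms would receive different numbers of replacements.

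What is at stake is the DNA-prime versus HA-F-prime comparison. Section 1.3 gives it as a reason for the design, 3.2 lists an antibody comparison by treatment and age group as a secondary objective, and 6.5.6 allows by-group results to inform later trials. Randomizing Part II protects that comparison only for subjects who were in fact randomized. No rule says that replacements are flagged or analysed apart from the rest.

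**Working it through.** **1. Scope.** Part I already has a same-group replacement sentence. The general rule comes after the Part II sentence, in the paragraph on Day 0 randomization, and speaks of any study group. It therefore reaches Groups 3 and 4. It does not say who allocates an added subject or by what mechanism.

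**2. The plan's own figures.** Table 6-3 gives the power of Fisher's exact test. Neither alpha nor sidedness is stated, so two-sided 0.05 is assumed. Full enumeration over two binomials gives, for 0.1 versus 0.5, 29.5% at n=10 (table: 30) and 74.2% at n=20 (table: 74). For 0.1 versus 0.6 it gives 47.4% and 90.8% (table: 47 and 91). All 30 distinct cells agree within one point. One-sided 0.05 does not fit (83.7% for 0.1 versus 0.5 at n=20). The table is sound, and this check only confirms the design on which replacement would act.

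**3. Shift in one arm's response rate.** Let n be the randomized subjects in the arm, k the replacements placed directly in it, and D the difference in response rate between the two kinds of subject. The documents give neither k nor D; k = 2 or 4 and D = 0.1 to 0.3 are assumptions.

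- All original subjects contribute a result: shift = k/(n+k) × D.
- The k leavers give no Week 18 sample: shift = k/n × D.

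| n | k | k/(n+k) | Shift, D = 0.1 to 0.3 | k/n | Shift, D = 0.1 to 0.3 |
|---|---|---|---|---|---|
| 20 | 2 | 2/22 = 9.1% | 0.009 to 0.027 | 10% | 0.01 to 0.03 |
| 20 | 4 | 4/24 = 16.7% | 0.017 to 0.050 | 20% | 0.02 to 0.06 |
| 10 (one age stratum) | 2 | 2/12 = 16.7% | 0.017 to 0.050 | 20% | 0.02 to 0.06 |

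Subjects who stop injections but stay in follow-up still give samples, so the actual shift lies between the two columns. The ceiling is all 65 − 40 = 25 extra subjects in one arm of 20: 25/45 × D = 0.056 to 0.167.

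**4. Type I error.** Fisher's test at two-sided 0.05, the same true rate in both randomized arms, k subjects with a rate 0.3 higher added to one arm, all originals kept:

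| k | Common rate 0.3 | Common rate 0.5 |
|---|---|---|
| 0 | 2.5% | 2.0% |
| 2 | 3.8% | 3.3% |
| 4 | 3.8% | 4.1% |
| 25 | 18.2% | 18.8% |

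Part of the rise at k = 2 and 4 comes from the changed sample size in a discrete test. With D = 0 the figures at rate 0.3 are already 3.6% and 2.9%.

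**5. Is same-group replacement needed for power?** For 0.1 versus 0.5:

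| Arm sizes | Power |
|---|---|
| 20/20 | 74.2% |
| 18/20 | 75.3% or 76.4%, depending on which arm is short |
| 16/20 | 70.1% or 74.1% |
| 18/18 | 66.8% |
| 21/21 | 75.9% |
| 22/22 | 78.6% |

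The 18/20 value exceeds the 20/20 value because the exact test is discrete. A modest imbalance costs little, and randomized additions restore numbers as well as placed ones do.

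**The case against.** The strongest reply is that 6.6 states no mechanism. The Part II rules that are written (a randomization plan prepared in advance by the statistician, concealment before enrollment, disclosure only after electronic enrollment) carry no exception for added subjects. A reader might infer that staff are authorized to choose a volunteer's arm; the text does not say so. This stands as a limit on the claim. Direct placement is the natural reading of adding a subject to a named group, but it remains a reading. What is firm is that the rule as worded cannot be followed literally in Part II while 4.2.3 is also honoured.

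A reader might also infer that the comparison is invalidated. The documents do not support that. Extra accrual is optional, 6.4.3 calls the comparison exploratory and says it is not powered at 10 per group, and the effect of a few replacements is small. The listing in 3.2 as a secondary objective keeps the point from being trivial.

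A third inference would be that replacement turns each arm into a set of completers. Section 6.5.4 retains all enrolled subjects by assigned group, and its stated exclusion concerns baseline antibody, not non-completion. Section 4.4.1 continues follow-up after one injection. A lost Week 18 sample is a missing-data matter with or without replacement.

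Nor is a damaged adverse-event comparison well founded. Section 6.4.1 mentions sample-size calculations for one, but 6.5.3 plans only tabulations, listings and boxplots. A concentration of late enrollees from another influenza season in one arm is possible, but nothing in the documents allows it to be sized.

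**Conclusion.** The point holds as a conflict between a stated rule and a stated safeguard. Section 6.6, read plainly, permits replacement into a known randomized arm on a post-randomization trigger, and 4.2.3 rules out advance knowledge of the arm. Subjects so placed would be analysed together with randomized ones, without distinction.

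The size is modest. With 2 to 4 replacements in one arm of 20 and an assumed D of 0.1 to 0.3, that arm's rate moves by about 0.01 to 0.05, or up to 0.06 at Week 18 if the leavers gave no sample. Type I error stays below 5%. Only the extreme case of all 25 extra subjects in one arm takes it to 18 to 19%. These figures rest on assumed values of k, D and alpha; no drop-out rate is stated. The change is worth making because same-group replacement brings no power that randomized addition would not.

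**What to change.** Limit same-group replacement in 6.6 to Part I. For Part II, state that each added subject receives the next assignment on the age-stratified randomization list, whichever arm that is, under the concealment rule of 4.2.3. Keep original subjects in their assigned groups, as 6.5.4 already provides. Flag added subjects in the analysis data set. If any were in fact placed directly, report a sensitivity analysis limited to the originally randomized subjects.

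The cost is one sentence in 6.6, a randomization list long enough for the 65 subjects that Table 2 permits, and one flag variable. Final arm sizes may differ by one or two; the block size, if any, is not given. At 18/20 the power for 0.1 versus 0.5 is 75 to 76%, against 74% at 20/20. The change removes allocation bias from added subjects. It does not address informative drop-out, which is a separate question.
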